15.4. Methods for Evaluation of Measurable Disease

All measurements should be taken and recorded in metric notation using a ruler or calipers. All baseline evaluations should be performed as closely as possible to the beginning of treatment and never more than 4 weeks before the beginning of the treatment.

The same method of assessment and the same technique should be used to characterize each identified and reported lesion at baseline and during follow-up. Imaging-based evaluation is preferred to evaluation by clinical examination unless the lesion(s) being followed cannot be imaged but are assessable by clinical exam.

Clinical lesions: Clinical lesions will only be considered measurable when they are superficial (e.g., skin nodules and palpable lymph nodes) and ≥ 10 mm diameter as assessed using calipers (e.g., skin nodules). In the case of skin lesions, documentation by color photography, including a ruler to estimate the size of the lesion, is recommended.

Chest x-ray: Lesions on chest x-ray are acceptable as measurable lesions when they are clearly defined and surrounded by aerated lung. However, CT is preferable.

Conventional CT and MRI: This guideline has defined measurability of lesions on CT scan based on the assumption that CT slice thickness is 5 mm or less. If CT scans have slice thickness greater than 5 mm, the minimum size for a measurable lesion should be twice the slice thickness. MRI is also acceptable in certain situations (e.g., for body scans).

Use of MRI remains a complex issue. MRI has excellent contrast, spatial, and temporal resolution; however, there are many image acquisition variables involved in MRI, which greatly impact image quality, lesion conspicuity, and measurement. Furthermore, the availability of MRI is variable globally. As with CT, if an MRI is performed, the technical specifications of the scanning sequences used should be optimized for the evaluation of the type and site of disease. Furthermore, as with CT, the modality used at follow-up should be the same as was used at baseline and the lesions should be measured/assessed on the same pulse sequence. It is beyond the scope of the RECIST guidelines to prescribe specific MRI pulse sequence parameters for all scanners, body parts, and diseases. Ideally, the same type of scanner should be used and the image acquisition protocol should be followed as closely as possible to prior scans. Body scans should be performed with breath-hold scanning techniques, if possible.

PET-CT: At present, the low dose or attenuation correction CT portion of a combined PET-CT is not always of optimal diagnostic CT quality for use with RECIST measurements. However, if the site can document that the CT performed as part of a PET-CT is of identical diagnostic quality to a diagnostic CT (with IV and oral contrast), then the CT portion of the PET-CT can be used for RECIST measurements and can be used interchangeably with conventional CT in accurately measuring cancer lesions over time. Note, however, that the PET portion of the CT introduces additional data which may bias an investigator if it is not routinely or serially performed.

Ultrasound: Ultrasound is not useful in assessment of lesion size and should not be used as a method of measurement. Ultrasound examinations cannot be reproduced in their entirety for independent review at a later date and, because they are operator dependent, it cannot be guaranteed that the same technique and measurements will be taken from one assessment to the next. If new lesions are identified by ultrasound in the course of the study, confirmation by CT or MRI is advised. If there is concern about radiation exposure at CT, MRI may be used instead of CT in selected instances.

Endoscopy/Laparoscopy: The utilization of these techniques for objective tumor evaluation is not advised. However, such techniques may be useful to confirm complete pathological response when biopsies are obtained or to determine relapse in trials where recurrence following complete response (CR) or surgical resection is an endpoint.

Tumor markers: Tumor markers alone cannot be used to assess response. If markers are initially above the upper normal limit, they must normalize for a patient to be considered in complete clinical response. Specific guidelines for both CA-125 response (in recurrent ovarian cancer) and PSA response (in recurrent prostate cancer) have been published [JNCI 96:487-488, 2004; J Clin

Version Date: 11/09/2017

Oncol 17, 3461-3467, 1999; J Clin Oncol 26:1148-1159, 2008]. In addition, the Gynecologic Cancer Intergroup has developed CA-125 progression criteria which are to be integrated with objective tumor assessment for use in first-line trials in ovarian cancer [JNCI 92:1534-1535, 2000].

Cytology/Histology: These techniques can be used to differentiate between partial responses (PR) and complete responses (CR) in rare cases (e.g., residual lesions in tumor types, such as germ cell tumors, where known residual benign tumors can remain).

The cytological confirmation of the neoplastic origin of any effusion that appears or worsens during treatment when the measurable tumor has met criteria for response or stable disease is mandatory to differentiate between response or stable disease (an effusion may be a side effect of the treatment) and progressive disease.

FDG-PET: While FDG-PET response assessments need additional study, it is sometimes reasonable to incorporate the use of FDG-PET scanning to complement CT scanning in assessment of progression (particularly possible 'new' disease). New lesions on the basis of FDG-PET imaging can be identified according to the following algorithm:

- Negative FDG-PET at baseline, with a positive FDG-PET at follow-up is a sign of PD based on a new lesion.
- No FDG-PET at baseline and a positive FDG-PET at follow-up: If the positive FDG-PET at follow-up corresponds to a new site of disease confirmed by CT, this is PD. If the positive FDG-PET at follow-up is not confirmed as a new site of disease on CT, additional follow-up CT scans are needed to determine if there is truly progression occurring at that site (if so, the date of PD will be the date of the initial abnormal FDG-PET scan). If the positive FDG-PET at follow-up corresponds to a pre-existing site of disease on CT that is not progressing on the basis of the anatomic images, this is not PD.
- FDG-PET may be used to upgrade a response to a CR in a manner similar to a biopsy in cases where a residual radiographic abnormality is thought to represent fibrosis or scarring. The use of FDG-PET in this circumstance should be prospectively described in the protocol and supported by disease-specific medical literature for the indication. However, it must be acknowledged that both approaches may lead to false positive CR due to limitations of FDG-PET and biopsy resolution/sensitivity.

Note: A 'positive' FDG-PET scan lesion means one which is FDG avid with an uptake greater than twice that of the surrounding tissue on the attenuation corrected image.

15.5. Response Criteria

NOTE: Clinical decision making can be made by irRECIST (that is, patients may be treated beyond progression) but the primary endpoint will be assessed by RECIST v. 1.1.

Assessment of Disease According to Immune Related RECIST for Solid Tumors

Version Date: 11/09/2017

The immune related RECIST (irRECIST), which is adapted to account for the unique tumor response seen with immunotherapies, will be applied for response evaluation.³⁴

The irRECST criteria considers index lesions identified at baseline together with new lesions that may occur after the start of treatment, and are incorporated into the calculated tumor burden. The appearance of new lesions alone does not constitute PD.

If imaging shows PD, tumor assessment should be repeated ≥4 weeks later to confirm PD with the option of continuing treatment for clinically stable subjects.

Confirmation of progression will be defined as a >10% increase in tumor burden on a subsequent scan (performed at ≥ 4 weeks) when compared to the initial progression scan.

In determining whether the tumor burden has increased or decreased, investigators should consider all target lesions as well as non-target lesions. Subjects who are deemed clinically unstable are not required to have repeat imaging for confirmation. If radiologic progression is confirmed, then the subject will be discontinued from study treatment as specified in the Protocol, and the first radiographic evidence of PD should be the date of progression. If radiologic progression is not confirmed, then the subject should resume/ continue study treatment and have their next scan according to the Protocol-specified schedule. If progression is not confirmed and the subject continues on treatment, the next scan that documents disease progression (and is confirmed by a second scan at least 4 weeks later) will be considered the date of disease progression.

15.5.1. Evaluation of Target Lesions by irRECIST

Tumor burden = Sum of diameter (target) + Sum of diameter (new)

Complete Response (CR): Disappearance of all target lesions. Any pathological lymph nodes (whether target or non-target) must have reduction in short axis to <10 mm.

Partial Response (PR): At least a 30% decrease in the tumor burden compared with baseline.

Progressive Disease (PD): At least a 20% increase in the tumor burden compared, taking as reference the smallest sum on study (this includes the baseline sum if that is the smallest on study), with confirmation of progression by a scan at least 4 weeks later (Note: With irRECIST, the appearance of new lesions alone is not considered progression).

Stable Disease (SD): Neither sufficient shrinkage to qualify for PR nor sufficient increase to qualify for PD, taking as reference the smallest sum diameters while on study.

15.5.2. Evaluation by Choi Criteria

Evaluation of response by Choi Criteria, which is a validated response criteria for GIST using change in radiographic density, will be performed for secondary endpoint analysis.

Version Date: 11/09/2017

"Size" refers to the change from the baseline of the sum of longest diameters of all target measurable lesions, as in RECIST criteria.

Complete Response (CR): Disappearance of all disease. No new lesions.

Partial Response (PR): A decrease in size of \geq 10% OR a decrease in CT density (HU) \geq 15%. No new lesions. No obvious progression of non-measurable disease.

Stable Disease (SD): Does not meet the criteria for CR, PR, or PD. No symptomatic deterioration attributed to tumor progression.

Progression of Disease (PD): An increase in uni-dimensional tumor size of \geq 10% AND did not meet criteria for PR by CT density. Any new lesions, including new tumor nodules in a previous cystic tumor.

15.6. Duration of Response

Duration of overall response: The duration of overall response is measured from the time measurement criteria are met for CR or PR (whichever is first recorded) until the first date that recurrent or progressive disease is objectively documented (taking as reference for progressive disease the smallest measurements recorded since the treatment started).

The duration of overall CR is measured from the time measurement criteria are first met for CR until the first date that progressive disease is objectively documented.

For patients who have not progressed or died, their follow-up will be censored at the time of last clinical evaluation.

Duration of stable disease: Stable disease is measured from the start of the treatment until the criteria for progression are met, taking as reference the smallest measurements recorded since the treatment started, including the baseline measurements.

15.7. Progression-Free Survival (PFS)

PFS is defined as the duration of time from enrollment to time of progression or death, whichever occurs first. For patients who have not progressed or died, their follow-up will be censored at the time of last clinical evaluation.

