Duration of administration	continuously during the study and for 90 days after the last dose of treatment. Subjects will be followed until all treatment related adverse events have recovered to baseline or are deemed irreversible by the investigator. Subjects who are removed from study for reasons other than progression of disease will be followed every 3 months with imaging to evaluate disease status and survival analysis while the study remains open. Continuous treatment, on 21 day cycles. Treatment will be continued until confirmed radiographic disease progression, intolerable side effects, or ongoing response at 2
Reference therapy	years of therapy. The reference therapy is salvage TKI therapy (sunitinib or regorafenib) in imatinib-refractory GIST patients, which has previously shown response rates of 7% and 5%, respectively.
Statistical Methodology	Definition of primary outcome/endpoint: The primary endpoint is the overall response rate as defined as the best response, confirmed at ≥4 weeks, within the first 24 weeks of the start of study therapy, using RECIST v1.1 criteria. Definition of secondary outcomes/endpoints: PFS is defined as time from registration to time of clinical or radiographic disease progression as defined by RECIST v1.1 criteria, or death. OS is defined as time from registration to time of death from any cause. Analytic plan for primary objective: We will estimate the response rate to combination therapy with epacadostat and pembrolizumab using the exact 95% confidence interval based on the binomial distribution. Analytic plan for secondary and exploratory objectives: • We will estimate the survival distribution for both PFS and OS endpoints using the Kaplan Meier method. The log rank test will be used to examine differences between survival curves. • For correlative studies we will apply either the Fisher's exact test or Wilcoxon rank sum test to examine the correlation between response status and markers for categorical and continuous variables, respectively.

Version Date: 11/09/2017

Sample size justification:

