12.2.1. Clinic Visits

During Cycle 1, patients will be seen weekly for vitals, physical exam, assessment of adverse effects, and appropriate laboratory tests and procedures (Section 13, Table 10 and table 11). Starting Cycle 2 and onward, patients will be seen on Day 1 of each cycle for vitals, physical exam, assessment of adverse effects, and appropriate laboratory tests and procedures. Patients may be seen for additional unscheduled visits as needed at the discretion of the investigator.

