12.2.2. Assessment for Serotonin syndrome

Subjects will be assessed for the presence of any of the following symptoms (Table 8) of serotonin syndrome at the time points indicated in the study calendar.

Table 8: Symptoms of Serotonin Syndrome

V 1
Tremor and hyper-reflexia
Spontaneous clonus
Muscle rigidity, temperature > 38 C, and either ocular clonus or inducible clonus
Ocular clonus and either agitation or diaphoresis
Inducible clonus and either agitation or diaphoresis

12.2.3. General laboratory assessment.

See Table 11 and 12 for detailed laboratory tests and timing of these tests.

12.2.4. Schedule of Disease monitoring.

A CT scan of the chest, abdomen, and pelvis with contrast will be obtained to evaluate disease status. A scan will be obtained at baseline (within 28 days of first study drug dose), then every 6 weeks for the first 24 weeks (imaging of the area with known disease involvement only (ex: CT chest only or CT abdomen/ pelvis only) is allowed for week 6 and week 18 tumor assessments at the investigator's discretion)). After week 24, a CT chest, abdomen, pelvis with contrast will be performed every 12 weeks until disease progression, withdrawal from study, or ongoing disease control at 2 years (defined as at least stable disease at this point). For patients who achieve ongoing disease control at 2 years, treatment will be stopped and subjects will be observed with a CT scan every 12 weeks. If the patient develops disease progression during this observation time, they will have the option of restarting study treatment at that time.

Table 9: Schedule of Disease Monitoring.

	_
Baseline scan	Baseline scan within 4 weeks prior to first treatment
Weeks 1 – 24	Every 6 weeks +/- 1 week (at weeks 6, 12, 18, 24)
Weeks 25 – until disease	Every 12 weeks +/- 1 week (at weeks 36, 48, 60, 72, 84, 96,
progression	108)

Columbia University Medical Center Herbert Irving Comprehensive Cancer Center Version Date: 11/09/2017

2 years	If subjects achieve ongoing disease control at 2 years, patients
	will be taken off study treatment and observed with imaging
	every 12 weeks +/- 2 week. If the patient develops disease
	progression, the option of re-initiating study therapy may be
	agneidared

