12.4. Follow-up Phase

12.4.1. Safety Follow-up

The safety follow-up phase is the interval between the last dose of study treatment and the scheduled safety follow-up visits, which should occur on days 30 (+/- 7 days) after the EOT visit. Adverse events and SAEs must be reported up until at least 90 days after the last dose of study drug, or until study drug-related toxicities resolve, return to baseline, or are deemed irreversible,

Version Date: 11/09/2017

whichever is longer. If a subject initiates a new anti-cancer therapy within 90 days after the last dose of study treatment, the next scheduled safety follow-up visit must occur before the first dose the new therapy. Once new anti-cancer therapy has been initiated, the subject will move into the survival follow-up phase.

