Concomitant medication review	X	X					
Comprehensive physical exam	X						
Targeted physical exam		X					
Assess for serotonin syndrome	X						
Vital signs and weight	X	X					
O2 saturation	X	X					
ECOG performance status	X	X					
AE assessment ¹	X	X ¹					
Laboratory assessments ³	X	X					
Radiologic tumor assessments	X 4		X 5				
Fresh tissue collection	X 6						
Blood for correlative studies	X 7						
Blood for PD analysis (fasting)	X 8						
Post-study anti-cancer therapy status			X	X			
Survival follow-up			X	X			

- 1. Subjects must be followed for AEs and SAEs for **90 days** after the last dose of study drug.
- 2. Subjects will be assessed by either a clinic visit or telephone contact every 12 weeks from the last dose of study treatment.
- 3. Safety laboratory assessments will be collected at EOT and at the each safety follow-up visit. See table 13 for detailed laboratory tests.
- 4. If a prior scan was obtained within 4 weeks before the date of discontinuation, then a scan at treatment discontinuation is not mandatory. In subjects who discontinue study therapy without confirmed disease progression, a radiological evaluation should be repeated at the time of treatment discontinuation (+/- 4 week window).
- 5. For subjects who discontinue treatment for reasons other than disease progression, every effort should be made to continue monitoring their disease status by radiographic imaging every 12 weeks until (1) start of new anticancer therapy, (2) documented disease progression, (3) death, or (4) the end of study, whichever occurs first.
- 6. An optional tumor biopsy sample for research purposes can be obtained at the time of disease progression.

- 7. See section 14.1.2 for instructions on blood collection for research correlative analysis.
- 8. See section 14.1.3 for instructions on blood collection for PD analysis.

Version Date: 11/09/2017

Table 13. Laboratory Assessments for End of Treatment and Follow-up Phase

	EOT	Follow-up Phase		
		Safety Follow-up		
PROCEDURE	+ 7 days	30 days after EOT +/- 7 days	Follow-up (Every 12 weeks) +/- 14 days	Survival Follow- up (Every 12 weeks) +/- 14 days
Chemistry ¹	X	X		
CBC w/ differential ²	X	X		
Liver function testing (LFT) ³	X	X		
TSH and Free T4 (FT4) and Total thriiodothyronine (T3)	X			
Urine or serum pregnancy test ⁴	X			
Blood for correlative studies ⁵	X			
Blood for PD analysis (fasting) ⁶	X			

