17. STATISTICAL CONSIDERATIONS

17.1. Study Endpoints and Analysis Plan

Definition of primary outcome/endpoint:

The primary endpoint is the overall response rate defined as the best response within the first 24 weeks of the start of study therapy using RECIST v. 1.1 that has been confirmed at a subsequent

time point (\geq 4 weeks).

Definition of secondary outcomes/endpoints:

PFS is defined as time from enrollment to time of clinical or radiographic disease progression as defined by RECIST v.1.1 criteria. OS is defined as time from enrollment to time of death from any cause.

Analytic plan for primary objective:

We will estimate the response rate to combination therapy with epacadostat and pembrolizumab using the exact 95% confidence interval based on the binomial distribution.

Analytic plan for secondary and exploratory objectives:

- We will estimate the survival distribution for both PFS and OS endpoints using the Kaplan Meier method. The log rank test will be used to examine differences between survival curves using prognostic markers such as KIT mutation status.
- For correlative studies we will apply either the Fisher's exact test or Wilcoxon rank sum test to examine the correlation between response status and markers for categorical and continuous variables, respectively. Because of the limited sample size, the biomarker data analysis is for exploratory research only.

Sample Size Justification

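### Section 17.1 leaves death out of PFS, against the synopsis and 15.7, and 15.7 censors at an undefined clinical evaluation with no stated rule for new anticancer therapy

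*Combined protocol and SAP*

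**What the plan says.** PFS is defined in three places.

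- Synopsis, Statistical Methodology: "PFS is defined as time from registration to time of clinical or radiographic disease progression as defined by RECIST v1.1 criteria, or death".
- Section 15.7: "PFS is defined as the duration of time from enrollment to time of progression or death, whichever occurs first".
- Section 17.1: "PFS is defined as time from enrollment to time of clinical or radiographic disease progression as defined by RECIST v.1.1 criteria". The sentence stops there, and the next one mentions death only for overall survival.

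The start point also differs: registration in the synopsis, enrollment in 15.7 and 17.1. The synopsis and 17.1 admit clinical as well as radiographic progression, while 15.7 says only progression.

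Section 15.7 has the only PFS censoring rule: "For patients who have not progressed or died, their follow-up will be censored at the time of last clinical evaluation". The documents do not define that evaluation. Section 17.1 has no censoring rule and specifies Kaplan-Meier estimation.

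On new anticancer therapy, Table 12 footnote 5 (Section 13) says that for patients who stop treatment without progression "every effort should be made to continue monitoring their disease status by radiographic imaging every 12 weeks until (1) start of new anticancer therapy". Section 12.4.2 also ends disease-status collection at that point, and 12.4.3 moves the patient to survival follow-up. These are follow-up rules. None of them says how PFS is analysed.

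**The concern.** An analyst is likely to program from Section 17.1. Read on its own, it describes time to progression, so a patient who dies without documented progression has no event. The synopsis and 15.7 would count that patient, so two analysts could draw different curves from the same data.

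The secondary objective is PFS by RECIST v1.1, which rests mainly on imaging. Censoring at a clinic visit credits progression-free time that no scan has confirmed. Without a rule for new therapy, the censoring date of a patient who switches treatment is left to the analyst.

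Both departures lengthen PFS or leave it unchanged. That direction is unhelpful in a single-arm trial whose background section quotes historical PFS medians.

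**Working it through.** **The plan's own figures.** The documents give no sample size, power or event count for PFS. The design figures concern response rate and reproduce exactly: stop if 0 of 12 respond, positive if at least 3 of 21 respond. Early stopping at a 5% response rate is 0.95^12 = 0.540 (stated 54%), type I error is 0.080 (limit 0.10), and power at 20% is 0.803 (stated at least 80%). None of these uses PFS.

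**Omitting death.** Assume all-cause PFS is exponential with a median of 27.3 weeks (the sunitinib figure in Section 3.1). Let f be the share of first events that are deaths without progression, constant over time and independent of progression. The documents give no f, so 5%, 10% and 20% are assumed.

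- True PFS at 24 weeks: S = exp(−ln 2 × 24/27.3) = 54.4%.
- Literal 17.1: S^(1−f), with median 27.3/(1−f).
- Expected deaths without progression by week 24 among 21 patients: 21 × (1 − 0.544) × f.

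| f | 24-week value under 17.1 | Shift (points) | Median (weeks) | Expected deaths |
|---|---|---|---|---|
| 5% | 56.1% | +1.7 | 28.7 | 0.5 |
| 10% | 57.8% | +3.4 | 30.3 | 1.0 |
| 20% | 61.4% | +7.0 | 34.1 | 1.9 |

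With the 4.8-month regorafenib median from the same section (20.9 weeks), S is 45.1% and the shift runs from +1.8 to +7.8 points.

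**Gap between last visit and last scan.** On treatment, Section 12.2.1 says "Starting Cycle 2 and onward, patients will be seen on Day 1 of each cycle", that is, every 3 weeks. Section 12.2.4 scans every 6 weeks to week 24, and then: "After week 24, a CT chest, abdomen, pelvis with contrast will be performed every 12 weeks until disease progression". On the nominal schedule the last visit can follow the last scan by 6 − 3 = 3 weeks before week 24 and by 12 − 3 = 9 weeks after it.

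Off treatment, Section 12.4.1 adds a safety visit, "which should occur on days 30 (+/- 7 days) after the EOT visit". Thirty days is 30/7 = 4.3 weeks, even with a scan on the day of the end-of-treatment visit. Table 12 footnote 4 waives that scan if one was done in the previous 4 weeks, so about 4 + 4.3 = 8.3 weeks is possible. If the 12-weekly telephone contacts in Table 12 footnote 2 counted as clinical evaluations, the gap would have no fixed limit after new therapy starts.

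**Effect of that gap.** I simulated 400,000 patients per scenario with a 27.3-week median and f = 10%. Progression was dated at the next scheduled scan and the data cut was uniform over weeks 52 to 104. Leavers stopped uniformly over weeks 0 to 24 and had the 30-day safety visit. Those who switched then had no further imaging. The 10% leaving figure borrows the dropout allowance in 17.1, taken here to mean leaving by week 24; 20% is assumed.

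24-week PFS, last visit minus last scan, in points (ranges are with and without an end-of-treatment scan; values for half switching are approximate):

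| Leave without progression | All switch | Half switch | None switch |
|---|---|---|---|
| 0% | 0.0 | 0.0 | 0.0 |
| 10% | +0.6 to +0.7 | +0.3 | 0.0 |
| 20% | +1.3 to +1.5 | +0.6 to +0.7 | 0.0 |

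At 48 weeks with all switching, the shifts are +0.3 to +0.4 (10%) and +0.7 to +0.9 (20%). The model dates every progression at a scan, so it does not test the effect of counting clinical progression.

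**Scale.** One patient in 21 is 4.8 points. The exact 95% interval for 11 of 21 is 29.8% to 74.3%, a half-width of about 22 points.

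**The case against.** The 17.1 omission looks like a drafting slip. Two of the three definitions count death, and the 15.7 censoring rule covers only patients who have neither progressed nor died, so it gives no authority to censor a death. A reader might infer that the plan means to analyse time to progression. The documents as a whole do not support that. What stands is that the statistical section disagrees with the other two and has to be reconciled. Section 17.3, which counts early deaths as treatment failures, does not settle the matter, because it is written for response rate.

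A clinical censoring date also has some logic. If clinical progression counts, a clinic visit does inform event status. Censoring only at scans while counting clinical progression found at visits would be lopsided. This stands, and the fix has to deal with it.

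A reader might also infer that the follow-up rules conflict over new therapy, because Section 5.1 describes 3-monthly imaging while the study remains open and names no such stop. That overstates it. Section 5.1 is general text and does not say imaging continues through a new therapy, while 12.4.2, 12.4.3 and Table 12 footnote 5 agree that disease-status follow-up ends there. Only the analysis rule is missing.

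**Conclusion.** The point holds as a minor one. Section 17.1 contradicts the synopsis and 15.7 on whether death is a PFS event, and 15.7 uses an undefined censoring date that can be later than the last scan. No PFS rule covers new therapy.

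The size rests on assumptions. The 1.7 to 7.0 point overstatement depends on the exponential model and the assumed death share, and applies only if 17.1 is followed literally. The censoring effect is nil when those who leave without progression stay on the imaging schedule, and its upper end is a worst case among the scenarios tried. All the shifts are small against a half-width of about 22 points, but they run in one direction.

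It would be wrong to infer any threat to the trial's decision. PFS is a descriptive secondary endpoint with no threshold or power, and the response-rate endpoint and two-stage rule do not use it.

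**What to change.** 1. Add death from any cause to the PFS definition in 17.1, so that it matches the synopsis and 15.7.
2. Use one start point throughout, registration or enrollment. The two should not be treated as interchangeable: Section 7.1 describes a pending registration soon after consent and a later confirmation of enrollment.
3. Censor event-free patients at the last adequate tumour assessment on or before the start of new anticancer therapy, and state this in both 15.7 and 17.1.
4. State whether clinical progression without imaging is an event. If it is, say how its date and the censoring date are kept consistent. One option is to take RECIST radiographic progression or death as the main PFS analysis and add clinical progression as an event in a sensitivity analysis.
5. Add a sensitivity analysis that counts new anticancer therapy as an event, since censoring at that point may be informative.

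The cost is a few wording changes and one or two extra descriptive analyses. The start date of new therapy must be available. Table 12 lists post-study therapy status, and the case report form is not in the documents, so the sponsor should confirm that the date is recorded. Reported PFS may come out slightly shorter. No sample size, threshold or visit schedule changes.
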